12. LIST OF TABLES, LISTINGS, AND FIGURES

Shells for unique tables, listings and figures are provided in a separate Mock-Up tables, figures, and listings (TFLs) document.

14. APPENDIX I. SCHEDULE OF ASSESSMENTS

TABLE 14-1 SCHEDULE OF ASSESSMENTS

Schedule of Assessments

Study Procedure	Screenin g Visit**		Treatment Period						
Cycle (C) #	-	Cycle 1				Cycle 2-13			
Cycle # and Day		C1D 1	C1D 8	C1D C1D1 C1D 8 5 22					
Window period (days)	-28 to -1 days	-1*	±1	±3	±3	±3 days	±7 days		
Informed consent ^a	Χ								
Demographics	Χ								
Eligibility screening	Χ	Χ							
Medical history ^b	Χ	Χ							
Physical examination ^c	Х	Х	Χ	Х	Х	Х	Х		
Height, weight ^d	Χ	Χ	Χ	Χ	Χ	Χ	Х		
Vital signs ^e	Χ	Х	Χ	Χ	Χ	X	Х		
ECOG ^f	Χ					C2D1 only	Х		
12-lead ECG ⁹	Χ	Χ	Χ			C2D1 only	Χ		
Pregnancy testing ^h	Χ						Χ		
Tumor biopsyi	X**								
Hematology and Biochemistry ^j	Х	Х	Х	Х	Х	Every 2 weeks (D1 and D15 of each Cycle)	Х		
Coagulation and Urinalysis ^k	Х	Х				Every 2 cycles, D1 (C2 C4, C6, C8, C10, C12)	Х		
Drug administration ^l		Х	Χ	Х	Χ	D1, D8, D15, D22 of each 28 day cycle			
Pharmacokinetic sample ^m		See	footn	ote m	and 7	Table 14-2 (Part A) and Table (Part B)	e 14-3		
Immunogenicity (ADA) ⁿ		See	footr	ote n	and T	able 14-2 (Part A) and Table (Part B)	14-3		
Biomarkers ^o	Х	See	footr	ote o	and T	able 14-2 (Part A) and Table (Part B)	: 14-3		
Radiology evaluations (CT or MRI) ^p	Х		End of every 2 cycles			х			
Concomitant medications	Х	Х	Х	Х	Х	X	Х		
Adverse events		Х	Χ	Χ	Χ	X	Χ		

EOS/ET - End of Study/Early Termination. EoS Visit is the safety follow-up visit, conducted

Review Status: Final Version: 2.0

Version Date: 02JUN2022

28±7 days after the last OBI-888 dose. ET visit lab assessments will be conducted for patients discontinuing study treatment, if last available tests are before 2 weeks.

*The - 1 day window (1 day prior) for C1D1 is for safety laboratory assessments. Blood can be drawn 1 day prior to initiation of study drug infusion on C1D1. Safety laboratory results should be available and reviewed by the Investigator prior to the OBI-888 administration.

** All patients are required to provide a tumor biopsy sample, unstained slides (preferred) or a FFPE tissue block at the initiation of screening visit for screening of Globo H overexpression and confirmation for eligibility of patients for Part B. Patients with a confirmed and documented Globo H H-score of ≥ 100 are eligible for the study, and will subsequently enter the 28-day screening period to complete the remaining screening procedures.

Footnotes:

- a. Informed consent to be obtained before any other study procedures are performed.
- b. Medical history to include previous cancer therapies, cancer history, and past and ongoing concomitant illnesses.
- c. A complete physical examination is required at screening and at discontinuation.

 Directed physical examinations may be limited to problem focused review of symptoms and major organ systems
- d. Height to be obtained at screening only.
- e. Vital signs include temperature, blood pressure and pulse (at supine position). Temperature measurement will be obtained as clinically indicated.
- f. ECOG performance status: at baseline, C2D1 and end of study/early termination
- g. 12-lead ECG: at screening and post infusion at C1D1, C1D8, and C2D1 (within one hour after end of infusion); and end of study/ early termination
- h. Pregnancy testing should be performed in females of childbearing potential only. A serum pregnancy test is required during screening. A urine or serum pregnancy test is acceptable end of study or early termination
- Tumor biopsy samples are mandatory at screening visit. Fresh (preferred) tissue or archival tissue is acceptable. A minimum of 3 slides are required for the central laboratory Globo H assay for determination of eligibility. Up to 12 unstained additional slides should be provided, depending upon availability, for the protocol-defined exploratory studies.
- j. Hematology and Serum chemistry (Laboratory Assessments: Protocol Table 12-1). Blood draw is prior to OBI-888 infusion.
 - Hematology: hematocrit, hemoglobin, erythrocyte count, white blood count (WBC), absolute counts of leukocytes, neutrophils, lymphocytes, monocytes, eosinophils, basophils, and platelet count. Serum chemistry: sodium, potassium, chloride, bicarbonate, BUN, creatinine, glucose, calcium, phosphorus, magnesium, total protein, albumin, ALT, AST, ALP, creatine kinase, LDH, total bilirubin, and uric acid. Creatinine clearance will be calculated by Cockcroft Gault equation at screen visit, week 1 and EOS/early termination.
- k. Coagulation, and Urinalysis (Laboratory Assessments: Protocol Table 12-1) Blood draw and urine collection is prior to OBI-888 infusion.
 Coagulation: PT, aPPT, and INR. Urinalysis: specific gravity, pH, protein, glucose, ketones, bilirubin, urobilinogen, blood, nitrite, leukocyte esterase as assessed by dipstick. A microscopic urinalysis (only if needed) evaluating white blood cells, red blood cells, epithelial cells, bacteria, cast and crystals
- I. OBI-888 is given in cycles with each individual cycle consisting of 28 days (4-week cycle). IP is administered on weekly basis (within cycle as C1D1, C1D8, C1D15, and

Review Status: Final Version: 2.0

Version Date: 02JUN2022

C1D22; C2D1, C2D8, and so on; for a total of 13 cycles, or disease progression or unacceptable toxicity, whichever occurs earlier.

- m. Pharmacokinetic: (for analysis of serum concentration of OBI-888). Detailed schedules are provided in Table 13-2 (Part A) and Table 13-3 (Part B).
- n. Immunogenicity studies (ADA) ADA samples will be collected at the same time points, along with pre-infusion only PK samples. No post-infusion ADA samples will be collected. Detailed schedules are provided in Table 13-2 (Part A) and Table 13-3 (Part B). For patients with persistent antibodies at end of study, an additional ADA sample will be collected at 4 months after the end of study visit.
- o. **Biomarker**: Detailed schedules are provided in Table 13-2 (Part A) and Table 13-3 (Part B).
- p. Radiology (CT or MRI scan) evaluations of tumor response: Performed during screening and during the study at the end of every second cycle (8 weeks) at: C2, C4, C6, C8, C10 and C12. CT or MRI scan will be performed within 1 week prior to the start of the next cycle. Unscheduled scan can be perform anytime, if needed to confirm disease progression. Radiology assessment for early termination/end of study, should only be performed if 8 or more than 8 weeks (≥8 weeks) have passed from the previous scheduled CT/MRI scan. Same assessment method and same technique should be used on each patient while on study.

Review Status: Final

Version: 2.0 Version Date: 02JUN2022

TABLE 14-2 PART A – PHARMACOKINETIC, ADA, BIOMARKER, AND GLYCAN SAMPLING SCHEDULE

Cycle (C)			Сус	de 1			Сус	le 2	Ever y 2 Cy cles ^{e,}	EoS / ET
Cycle Day	D1	D2	D4	D8	D15	D2 2	D1, 8, 15	D22	D1	±7 days
Pharmacokinetic Samples										
Before infusion	Xa			Xb	Xp	Xb	Xp	Xp	Xp	Χ
End of infusion (90 minutes) ^c	Х	Xd	Xd	Х	Х	Х	х	Х		
1 hour after end of infusion (150 minutes) ^e	Х									
4 hours after end of infusion (330 minutes) ^e	Х									
8 hours after end of infusion (570 minutes) ^e	Х									
Immunogenicity studies (ADA) ^f	Х			Х	Х	Х	Х	Х	Х	Х
Glycan analysis ^g	Χ			Χ	Х	Х	Х	Х		
Biomarkers										
ADCC ⁱ	Χ				Х			Х	C4D1	Х
CDC/ADCC ⁱ	Χ			Χ	Х					
KIR, HLA, Fc receptor gamma genotyping ⁱ	Х							_		Х

ADA = antidrug antibody; ADCC = antibody-dependent cell-mediated cytotoxicity; C = cycle; CDC = complement dependent cytotoxicity; D = day; EoS/ET = End of Study/Early Termination; HLA = human leukocyte antigen; KIR = killer cell immunoglobulin-like receptor Note: OBI-888 infusion should be administered on Days 1, 8, 15, and 22 of every 28-day cycle throughout the study treatment period.

The infusion duration of Cycle 1 and Cycle 2 are 90 minutes, and can be reduced to 30-60 minutes for Cycle 3, if there were no infusion related adverse events on prior infusions and at the discretion of the investigator.

- a. C1D1 Pre-infusion serum samples can be drawn within 1 day prior-to the infusion.
- b. Pre-infusion serum samples can be collected at any time prior to the infusion on the day of the infusion.
- c. Post infusion samples at the end of infusion and later (at 1, 4, and 8 hours after the end of the infusion) can be collected in a window of ± 15 minutes.
- d. For Cycle1 Days 2 and 4, a single sample will be collected (window ± 2 hours):
 - 24 hours after end of infusion (for infusion at C1D1)

Review Status: Final Version: 2.0 Version Date: 02JUN2022

• 72 hours after end of infusion (for infusion at C1D1)

- e. If there is change of the infusion rate or interruption of infusion, the PK sampling at Day 1 are to be collected from the exact time of completion of infusion to obtain the post-infusion samples at 1, 4, 8 hour at the end of infusion. Exact time of sample collection and the reason for interruption should be documented in the eCRF.
- f. ADA sample will be collected along with the pre-infusion PK samples according to the above table. No post-infusion ADA samples including C1D2 and C1D4 will be collected. For patients with persistent antibodies at end of study, an additional ADA sample will be collected at 4 months after the end of study visit.
- g. Glycan analysis: pre-infusion and end of infusion in cycle 1 and 2 only. Residual PK and ADA samples will be pooled for glycan analysis after PK and ADA data are finalized.
- h. Samples to be collected on Day 1 of C4, C6, C8, C10, C12.
- Biomarkers:
 - ADCC (effector cell): pre-infusion blood sample will be collected at C1D1, C1D15, C2D22, C4D1 and end of study/early termination.
 - CDC/ADCC (humoral): pre infusion and end-of-infusion blood sample will be collected at C1D1, C1D8, and C1D15.
 - KIR, HLA, Fc receptor gamma genotyping: blood sample will be collected at C1D1 (pre-infusion) and end of study/early termination.

TABLE 14-3 PART B – PHARMACOKINETIC, ADA, AND BIOMARKER SAMPLING SCHEDULE

Cycle (C)	Scree ning	Cycle 1			Cy cle 2	Every 2 cycle s starti ng with Cycle 3 a	Every 2 cycl es starti ng with Cycle 4°	EoS / ET			
Cycle Day	-28 to -1 days	D 1	D2	D4	D 8	D 1 5	D2 2	D1	D1	D1	±7 days
Pharmacokinetic Samples											
Before infusion		X^d			Xb	Xb		Xp		Xb	
End of infusion (90 minutes) ^f		X	X ^{j,k}	X ^k		Х					
1 hour after end of infusion (150 minutes) ^{e,f}		Χ ^j									
3 hours after end of infusion (270 minutes) ^{e,f}		Χ ^j									
6 hours after end of infusion (450 minutes) ^{e,f}		X ^j									
Immunogenicity studies (ADA) ^g		Χ						Х		Х	Χ
Glycan analysish		Χ			Χ	Χ		Х		Χ	Χ
Biomarkers											
Globo H	X										
ADCC/CDC (humoral) ^{d,l}		Χ			Χ	Х					
KIR, HLA, Fc receptor gamma genotyping ^d		Х									
Multiplex IHC ⁿ	Х										
Diagnostic marker ⁿ	X										

Review Status: Final Version: 2.0 Version Date: 02JUN2022

SSEA-3/SSEA-4 ⁿ	Χ						
Surrogate biomarker ^{d,i}		Х				Х	

ADA = antidrug antibody; ADCC = antibody-dependent cell-mediated cytotoxicity; C = cycle; CDC = complement dependent cytotoxicity; D = day; EoS/ET = End of Study/Early

Termination; HLA = human leukocyte antigen; IHC = immunohistochemistry; KIR = killer cell immunoglobulin-like receptor; SSEA = stage-specific embryonic antigens

Note: OBI-888 infusion should be administered on Days 1, 8, 15, and 22 of every 28 day cycle throughout the study treatment period.

The infusion duration of Cycle 1 and Cycle 2 are 90 minutes, and can be reduced to 30-60 minutes from Cycle 3, if there were no infusion related adverse events on prior infusions and at the discretion of the investigator.

- a. Samples to be collected on Day 1 of C3, C5, C7, C9, C11, and C13.
- b. Pre-infusion serum samples can be collected at any time prior to the infusion on the day of the infusion.
- c. Samples to be collected on Day 1 of C4, C6, C8, C10, and C12.
- C1D1 Pre-infusion serum samples can be drawn within 1 day prior-to the infusion.
- e. If there is change of the infusion rate or interruption of infusion, the PK sampling at Day 1 are to be collected from the exact time of completion of infusion to obtain the post-infusion samples at 1, 3, 6 hour at the end of infusion. Exact time of sample collection and the reason for interruption should be documented in the eCRF.
- f. Post infusion samples at the end of infusion and later (at 1, 3, and 6 hours after the end of the infusion) can be collected in a window of ± 15 minutes
- g. ADA sample will be collected along with the pre-infusion PK samples according to the above table. For patients with persistent antibodies at end of study, an additional ADA sample will be collected at 4 months after the end of study visit.
- Glycan analysis: Residual PK and ADA samples will be pooled for glycan analysis after PK and ADA data are finalized.
- Samples should be collected to evaluate tumor-specific biomarkers (eg, CEA for colorectal, gastric, and esophageal cancer; and CA19-9 for pancreatic cancer).
- j. This intensive PK sampling will be collected only from first 3 patients in each cohort.
- k. For C1D2 and C1D4, samples can be collected in a window of ± 2 hours:
 - 24 hours after end of infusion (for infusion at C1D1).
 - 72 hours after end of infusion (for infusion at C1D1).
- II. Blood sample will be collected pre-infusion and end-of-infusion.
- m. Blood sample will be collected pre-infusion.
- Tumor biopsy samples obtained during the initial screening visit should be used for this assessment.

15. APPENDIX II IMPUTATION RULES FOR MISSING DATES

Algorithm for Treatment-emergent Adverse Events

Algorithm for Treat		Auverse Evenis
AE Start Date	AE Stop Date	Action
Known	Known	If start date < study drug start date, then not TEAE
		If start date ≥ study drug start date, then TEAE
	Partial	If start date < study drug start date, then not TEAE
		If start date ≥ study drug start date, then TEAE
	Missing or	If start date < study drug start date, then not TEAE
	Unknown	If start date ≥ study drug start date, then TEAE
Partial, but the known	Known	Not TEAE
date components show		
that it cannot be on or	Partial	Not TEAE
after study drug start	Missing or	Not TEAE
date	Unknown	
Partial, could be on or	Known	If stop date < study drug start date, then not TEAE
after study drug start		If stop date ≥ study drug start date, then TEAE
date	Partial	Impute stop date as latest possible date (i.e., last day of
		month if day is unknown or 31-Dec if day and month are
		unknown), then:
		If stop date < study drug start date, then not TEAE
		If stop date ≥ study drug start date, then TEAE
	Missing or	Assumed TEAE
	Unknown	
Missing or	Known	If stop date < study drug start date, then not TEAE
Unknown		If stop date ≥ study drug start date, then TEAE
	Partial	Impute stop date as latest possible date (i.e., last day of
		month if day is unknown or 31st December if day and month
		are unknown), then:
		If stop date < study drug start date, then not TEAE
		If stop date ≥ study drug start date, then TEAE
	Missing or	Assumed TEAE
	Unknown	

Version Date: 02JUN2022

Algorithm for Concomitant Medications

CM Start Date	CM Stop Date	Action
Known	Known	If stop date < study drug start date, assign as PRIOR If stop date ≥ study drug start date, assign as CONCOMITANT
	Partial	Impute stop date as latest possible date (i.e., last day of month if day unknown or 31-Dec if day and month are unknown), then: If stop date < study drug start date, assign as PRIOR If stop date ≥ study drug start date, assign as CONCOMITANT
	Missing or Unknown	Assign as CONCOMITANT
Partial	Known	If stop date < study drug start date, assign as PRIOR If stop date ≥ study drug start date, assign as CONCOMITANT
	Partial	Impute stop date as latest possible date (i.e., last day of month if day unknown or 31-Dec if day and month are unknown), then: If stop date < study drug start date, assign as PRIOR If stop date ≥ study drug start date, assign as CONCOMITANT
	Missing or Unknown	Assign as CONCOMITANT
Missing or Unknown	Known	If stop date < study drug start date, assign as PRIOR If stop date ≥ study drug start date, assign as CONCOMITANT
	Partial	Impute stop date as latest possible date (i.e., last day of month if day unknown or 31-Dec if day and month are unknown), then: If stop date < study drug start date, assign as PRIOR If stop date ≥ study drug start date, assign as CONCOMITANT
	Missing or Unknown	Assign as CONCOMITANT

Review Status: Final Version: 2.0

Version Date: 02JUN2022

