13.3 Glycan Analysis of OBI-888

Glycan analysis of the Fc portion of OBI-888 mAb will be performed in the pre-infusion and end of infusion samples in the first two cycles of treatment (see Table 9-2 [Part A – Dose Escalation] and Table 9-3 [Part B – Expansion]). Residual samples from the PK and ADA analyses samples will be pooled for glycan analysis after PK and ADA data are finalized.

Fc-glycans and the terminal sugars of Fc-glycans have been shown to be critical for the safety, PK and efficacy (ADCC) of mAb. If the Fc-glycans are completely hydrolyzed, the mAb may lose its ADCC activity and anti-tumor efficacy. Modification of Fc-glycans and glycosylation patterns may influence the PD and PK behavior of OBI-888. Therefore, these exploratory glycan analysis data on OBI-888 may be used to correlate with its clinical efficacy.

14 Statistical Analysis

A Statistical Analysis Plan (SAP) will be prepared after the protocol is approved. This document will provide further details regarding the definition of analysis variables and analysis methodology to address all study objectives. The SAP will serve as a compliment to the protocol and supersedes it in case of differences.

The statistical evaluation will be performed using the Statistical Analysis Software (SAS[®]) Version 9.4 or higher (SAS Institute, Cary, NC).

Analyses will be conducted by dose level in the dose escalation phase and by cohort in the expansion phase. Descriptive summaries for categorical variables will include counts and percentages. Descriptive summaries for continuous variables will include means, medians, standard deviations, minimum and maximum values. Descriptive summaries of time to event data will include medians and confidence intervals. Graphical summaries of the data may be presented. All data will be listed for all patients.

Further details of the analysis, including the handling of missing data, transformations, other data handling procedures, and analytical methodology will be provided in the SAP. Additional exploratory analyses of the data will be conducted as deemed appropriate.

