14.5 Safety Analysis

AEs will be coded according to Medical Dictionary for Regulatory Activities (MedDRA) version 19.0 or higher and assessed for severity using CTCAE version 4.03. AEs will be summarized by system organ class and preferred term and presented in decreasing order of incidence. DLTs will also be summarized by dose and cohort. The incidence of TEAEs (events with onset dates on or after the start of the study drug) will be included in incidence tables. Events with missing onset dates will be included as treatment-emergent. If a patient experiences more than 1 occurrence of the same AE, the occurrence with the greatest severity and the closest association with the study drug will be used in the summary tables. SAEs and AEs causing discontinuation will be tabulated. All AEs will be listed by patient, along with information regarding onset, duration, relationship and severity to study drug, action taken with study drug, treatment of event, and outcome.

Vital signs, ECG data, hematology, serum chemistry, coagulation, and urinalysis parameters from baseline and during study will be examined. Treatment emergent changes in key laboratory parameters will be identified. Clinical laboratory data and vital signs will be summarized for each time point evaluated using descriptive statistics including mean values and mean change from baseline values, as well as numbers of patients with values outside limits of the normal range at each time point.

Summary tables will be provided for concomitant medications initiated prior to study enrollment or during the study period.

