8. ANALYSIS ENDPOINTS

Analysis endpoints are listed as per protocol. Only those endpoints marked with * will be analyzed in the aCSR. Exploratory analyses are to be conducted by OBI Translational Biology (or their designee) and may be included as appendices in the aCSR.

8.1 PRIMARY ENDPOINTS:

- DLTs with OBI-888*.
- AEs/ serious AEs (SAEs) and laboratory abnormalities as graded by National Cancer Institute Common Terminology Criteria for Adverse Events (NCI CTCAE) version 4.03*.
- MTD and RP2D of OBI-888.

8.2 SECONDARY ENDPOINTS:

- Percentage of patients with ORR, CBR*, DOR and PFS according to Response Evaluation Criteria in Solid Tumors version 1.1 (RECIST 1.1).
- Percentage of patients with anti-OBI-888 ADAs in blood*.
- PK and PD parameters of OBI-888*.

8.3 EXPLORATORY ENDPOINTS:

- Globo H and related glycan expression in tumor tissue by IHC.
- ADCC and CDC.
- Identify potential predictive markers by IHC or molecular analysis.
- Tumor Infiltrating Lymphocytes (TILs) including natural killer (NK) cells, and programmed death ligand 1 (PD-L1) expression in tumor tissue samples by IHC.
- Killer cell immunoglobulin-like receptor (KIR), human leukocyte antigen (HLA), and Fc receptor gamma genotype.
- Glycan analysis of OBI-888.

Review Status: Final Version: 2.0 Version Date: 02JUN2022

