10.3 HANDLING OF MISSING DATA

For the calculation of the time since initial cancer diagnosis, the following imputation rules will be applied when the date of initial cancer diagnosis is incomplete:

- If the day is missing: first day of the month.
- If the day and month are missing: first day of January.

Partial or missing start and end dates of AEs and concomitant medications will be imputed conservatively based on the rule described in Appendix II: Imputation rules for missing dates. The imputed dates will be used to allocate the AEs and concomitant medications to a study period, and to determine whether an AE is/is not treatment emergent. Listings of the AEs and concomitant medications will present the actual partial dates; imputed dates will not be shown.

For CBR endpoint, patients with missing data (for any reason) will be included as non-responder.

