10.7.1 PRIMARY ENDPOINTS

A. DLTs with OBI-888

The period for DLT is 28 days from the start of first dose of Investigational Product at Day 1 in study part A.

A DLT is defined as the occurrence of any of the following events within the first cycle of treatment and are considered to be at least possibly related to OBI-888:

- Grade 4 neutropenia
- Grade ≥ 3 febrile neutropenia with or without infection
- Grade 4 thrombocytopenia
- Grade ≥ 3 nausea and vomiting or diarrhea for more than 72 hours despite optimal supportive care
- Any Grade ≥ 3 non-hematological AE, except for nausea, vomiting, or diarrhea that does not resolve before the next infusion
- Grade 4 infusion reactions, and Grade ≥ 3 infusion reactions that recur despite decreasing infusion rate and optimal supportive care measures

DLTs will be displayed by assigned dose and cohort in a frequency table in decreasing order of incidence. DLTs will not be programmatically derived but analyzed as collected on the eCRF.

AE terms will be coded using the most current version of the Medical Dictionary for Regulatory Activities (MedDRA). AEs will be graded according to the NCI CTCAE version 4.03. All AEs unless they have been determined to be not related to study drug will be taken into consideration in determining DLTs.

B. AEs/SAEs and laboratory abnormalities as graded by NCI CTCAE version 4.03

A treatment-emergent adverse event (TEAE) is defined as an AE with onset dates on or after the start of study drug or if it is present prior to receipt of the study treatment but worsens in severity or increases in frequency on or after the first dose. AEs having both onset and end dates missing will be considered as TEAEs.

Events reported as "Unrelated" or "Unlikely related" to study drug will be considered as unrelated to the study drug. Events reported as "Possibly related", "Probably related", "Definitely related" to study drug or without relationship information will be considered as related to the treatment.

Tables will display the incidence of events (number of events, number of patients with any event, number of patients with any event in each specific system organ class [SOC], and number of patients with any event for each specific preferred term [PT]).

For each AE, only the highest grade and closest association with study drug by patient will be considered in the incidence analyses.

The following tables will be produced:

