Tables by SOC and PT will be displayed for following AEs. Only those AEs marked with * will be

Review Status: Final Version: 2.0 Version Date: 02JUN2022

analyzed in the aCSR:

- DLTs
- Treatment-emergent adverse events (TEAEs)*
- TEAEs grade ≥ 3*
- TEAEs related to OBI-888*
- TEAEs leading to discontinuation of OBI-888*
- Serious TEAEs
- Serious TEAEs related to OBI-888*
- AEs leading to discontinuation of OBI-888
- SAEs leading to discontinuation of OBI-888
- TEAEs leading to death*

A table of TEAEs by SOC, PT and worst CTCAE grade (per summarization level) will be presented.

The following listings will be prepared:

- · All AEs, with DLTs flagged
- All SAEs
- AEs related to OBI-888
- AEs grade ≥ 3
- All TEAEs leading to OBI-888 discontinuation
- AEs leading to death
 - C. MTD and RP2D of OBI-888

The MTD and RP2D were identified as 20 mg/kg during SRC review.

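### The SAP defines a worsened pre-existing event as treatment-emergent, but the Appendix II algorithm that sets the flag never tests for worsening when the start date is certainly pre-dose

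*SAP*

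**What the plan says.** **Definition.** SAP section 10.7.1, part B, has two limbs. An event is treatment-emergent if it starts once study drug has started. The second limb adds any event "present prior to receipt of the study treatment but worsens in severity or increases in frequency on or after the first dose".

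**Algorithm.** SAP section 10.3 handles incomplete AE dates through Appendix II and uses the result "to determine whether an AE is/is not treatment emergent". Appendix II also covers complete dates. For a known start date its rule is "If start date < study drug start date, then not TEAE", repeated for known, partial and missing stop dates. A separate block covers partial start dates whose known parts show "that it cannot be on or" after first dosing, and it also returns not TEAE for all three kinds of stop date.

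**Protocol.** Protocol section 14.5 has the onset limb only: "The incidence of TEAEs (events with onset dates on or after the start of the study drug) will be included in incidence tables". The opening of protocol section 14 says that the SAP "supersedes it in case of differences".

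**Use of the flag.** SAP section 8.1 lists among the primary endpoints "AEs/ serious AEs (SAEs) and laboratory abnormalities as graded by National Cancer Institute Common Terminology Criteria" for Adverse Events. In SAP section 10.7.1, six tables by system organ class and preferred term are starred for the abbreviated report. All six are TEAE tables, "TEAEs grade ≥ 3" among them.

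**The concern.** The two rules give different answers for the same record. Under the definition, a Grade 1 symptom present at baseline that becomes Grade 3 in Cycle 2 is a TEAE. Under the algorithm, a row for it that carries its baseline start date is not. Because the conflict lies inside the SAP, the SAP's precedence over the protocol does not settle it, and two programmers could produce different tables from the same data.

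AEs are a primary endpoint, and SAP section 3 says that the abbreviated report focuses on safety and exposure. Exclusion criterion 7 lets patients enter with Grade 1 residual toxicity, so worsening of something already present is an ordinary way for toxicity to appear. For worsened events with a certainly pre-dose start, the algorithm can only remove counts.

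**Working it through.** The plan gives no figure to reproduce here. The check compares the two rules case by case, taking first dose as day 0.

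**Rule A (SAP 10.7.1).** TEAE if onset is on day 0 or later, or if onset is earlier and the event worsens in severity or frequency from day 0.

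**Rule B (SAP Appendix II).** Known start: TEAE only if the start is on day 0 or later. Partial start that must be pre-dose: not TEAE. Partial start that could be on day 0 or later, or missing start: TEAE if the latest possible stop date is on day 0 or later, or if the stop date is missing.

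Each start type is crossed with three stop types (known and on treatment; partial with its latest possible date on treatment; missing) and with worsening yes or no.

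| Start date | Worsens on treatment | Combinations | TEAE, rule A | TEAE, rule B |
|---|---|---|---|---|
| Known, pre-dose | yes | 3 | 3 | 0 |
| Partial, certainly pre-dose | yes | 3 | 3 | 0 |
| Either of the above | no | 6 | 0 | 0 |
| Known, on or after first dose (two dates tried) | yes and no | 12 | 12 | 12 |
| Partial, could be on or after first dose; true onset assumed pre-dose | yes | 3 | 3 | 3 |
| Same | no | 3 | 0 | 3 |

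**Result.** For a certainly pre-dose start with worsening, rule A gives 3 + 3 = 6 of 6 and rule B gives 0 of 6. For a known start on or after first dose, the rules agree in all 12 combinations. The last row differs the other way. It is a cautious default for unclear dates and is not part of this point. Together these rows mean that a worsened event is counted when its start date is vague and dropped when its start date is known.

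**Which records can reach the pre-dose rows.** Under protocol section 12.5.1, AE collection runs from first dose, conditions present at screening go to medical history, and changes in them go on the AE form. Protocol section 8.6.1 has worsening of a concomitant illness documented as an AE, without saying which onset date to enter. The text after Table 12-3 asks for separate records with distinct onset dates when intensity changes over days, but does not mention frequency. Two kinds of record remain exposed: increases in frequency, and worsened conditions entered with their original onset date.

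**Illustration of size only.** No Part A cohort enrolment is stated. Protocol section 4.3.1 gives ADA results as 1/5 and 1/3 for the first two cohorts and 14 patients in Part A. If the ADA denominators are the cohort sizes, the third cohort has 14 − 5 − 3 = 6. One patient lost from a table row then lowers that incidence by 1/5 = 20, 1/3 = 33 or 1/6 = 17 percentage points. In a Part B cohort at its first-stage ceiling of 9, the drop is 1/9 = 11 points. All of these assume that the patient has no other qualifying record in that row. They say nothing about how many patients are affected.

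**The case against.** The strongest reply is that the pre-dose rows should be nearly empty. The protocol keeps the baseline condition in medical history and puts the change on the AE form, so the AE record is normally the worsening itself and has an on-treatment onset that Appendix II counts. The instruction to record changes is not limited to severity, so it arguably reaches frequency as well. A wrong flag would then need a site to enter the old onset date. This largely stands, and it is why no size can be claimed. It does not close the gap: the protocol does not say which onset date a worsened condition takes, and the only explicit instruction on distinct onset dates concerns intensity.

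It can also be argued that Appendix II is only an imputation aid and that section 10.7.1 governs. But its rows for fully known dates have nothing to impute and return a final classification, and nothing in the SAP limits them to the onset limb.

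A reader might infer three stronger things, none of which the documents support:

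- *That every AE with a pre-dose start is rejected.* Partial or missing starts that could fall after first dose become TEAEs when the stop date is on treatment or missing.
- *That worsening of the abnormal blood counts or liver enzymes allowed at entry would go unseen.* SAP section 10.8.2 keeps laboratory tables by visit and CTC grade and by worst post-baseline grade, without the TEAE flag. SAP section 11 does drop the shift tables, so the change from each patient's baseline grade is less direct to read.
- *That events would be hidden.* The listings of all AEs, all SAEs, related AEs, Grade 3 or higher AEs and AEs leading to death are not restricted to TEAEs. An event could be missing from an incidence table but would still be listed.

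**Conclusion.** The inconsistency is real and internal to the SAP. For a known or certainly pre-dose start, Appendix II cannot return the TEAE status that section 10.7.1 requires when the event worsens (0 of 6 date patterns against 6 of 6). It bears on all six starred TEAE tables, and any resulting error is an under-count.

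Its effect on the results is unknown and may be zero. That depends on how sites dated worsened conditions and recorded increases in frequency, which the documents do not show. DLTs are taken as collected on the eCRF and are unaffected, as are the CTC-grade laboratory tables and the all-AE listings. This is a rule to reconcile before the tables are final, not a demonstrated bias.

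**What to change.** Choose one of two changes.

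1. In the pre-dose rows of Appendix II (known start, and partial start that is certainly pre-dose), add: *if severity or frequency increased from first dose onward, then TEAE, graded at the worst on-treatment grade; otherwise not TEAE.*
2. In section 10.7.1, state that any worsening of a pre-existing event, frequency included, is a new AE record with its own onset date, and that this record is what the algorithm tests.

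In either case, review all AE rows with pre-dose start dates before database lock and report how many there are. That count settles whether the point has any effect.

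The cost is small: SAP wording and, for the first option, one programming condition. It may not be free of data work. Where one row spans baseline and treatment, the AE items listed in protocol section 12.5.1 include no baseline grade or date of worsening, so a few site queries may be needed.
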